1. PROTOCOL OVERVIEW

Protocol Title:	Baricitinib in relapsing giant cell arteritis (GCA): a phase II, single-institution, open-label pilot study
Study Chairs:	[name]. – Principal Investigator [name]. – Co-Principal Investigator
Statistician:	[name], M.S.
Study Coordinator:	[name], C.C.R.C.
Participating Sites:	Mayo Clinic, Rochester, MN
Activation Date:	1/1/2017
Sample Size:	15
Target Enrollment Period:	60 weeks
Study Design:	Open-label, Phase II
Primary objective:	To determine the safety and tolerability of baricitinib, 4mg oral daily, in GCA
Secondary objective	To gather preliminary data on the efficacy of baricitinib, 4mg oral daily, in patients with relapsing GCA 
 • Relapse-free survival at week 52 • Relapse-free survival at week 24 • Duration of glucocorticoid-free remission • Number of relapses per subject over time • Change from baseline erythrocyte sedimentation rate (ESR) to end of study • Change from baseline C-reactive protein to end of study • Glucocorticoid dose (mg) at week 52 compared to enrollment • Change in BVAS from baseline to end of study
Inclusion criteria	1. Diagnosis of GCA defined by the following Revised GCA Diagnosis Criteria: 
 • Age \geq50 years. • History of ESR \geq 50 mm/hour or CRP \geq 10 mg/L. • Presence of at least one of the following: 
 ○ Unequivocal cranial symptoms of GCA (new onset localized headache, scalp or temporal artery tenderness, otherwise unexplained mouth or jaw pain upon mastication). ○ Unequivocal symptoms of PMR, defined as shoulder and/or hip girdle pain associated with inflammatory stiffness. ○ Systemic inflammatory disease in which the presence of the fever ($>$38 degrees Celsius for \geq 7 days), weight loss ($>$ 5 lbs or 10% premorbid weight), and/or night sweats were attributable to GCA and no other cause was

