3.6. Baricitinib in Giant Cell Arteritis

Cytokines and mediators that have been associated with aberrant autoimmunity and increased inflammatory responses in GCA include IL-6, IL-12, IL-23, and interferon γ (IFN- γ). These cytokines signal through the JAK family (JAK1, JAK2, JAK3 and tyrosine kinase 2 [Tyk2]) [37]. Baricitinib is an oral Janus kinase inhibitor with preferential inhibition of JAK1 and JAK2. IL-6 and IFN- γ primarily signal through JAK1 and IL-12 and IL-23 through JAK2. Therefore an agent that preferentially inhibits both JAK1 and JAK2 will provide reduction of intracellular signaling through multiple proinflammatory pathways, reducing activity of both pathologic Th17 and Th1 cell lineages.

Given these findings, an open-label phase II trial of baricitinib in patients with relapsing GCA is proposed. The purpose of this study will be to evaluate the safety and preliminary efficacy of baricitinib in treatment of patients with relapsing GCA.

4. OBJECTIVE(S) and ENDPOINT(S)

Objectives	Endpoints/Measures
Primary	

 To investigate the safety of baricitinib, 4 mg oral daily for duration of 52 weeks, administered to patients with relapsing GCA in combination with a standardized glucocorticoid taper 	
 Incidence of adverse effects and serious adverse effects, changes in hematology and clinical chemistry patterns
Secondary	

 To evaluate preliminary efficacy of baricitinib, 4 mg oral daily for duration of 52 weeks, administered to patients with relapsing GCA in combination with a standardized glucocorticoid taper 	
 Relapse-free survival at week 52 Relapse-free survival at week 24 Duration of glucocorticoid-free remission

	
 • Duration of glucocorticoid-free remission • Number of relapses per subject over time • Change from baseline erythrocyte sedimentation rate to end of study • Change from baseline C-reactive protein to end of study • Glucocorticoid dose (mg) at week 52 compared to baseline • Change in BVAS from baseline to end of study
--	---

[figure not shown]

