5.1.2. Design Overview

- A screening phase of up to 6 weeks in duration
- 52-week open-label study drug treatment phase with standardized prednisone taper
- A 12-week follow-up phase to ensure that all subjects are evaluated for safety at 12 weeks after receiving the last dose of study drug.

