To be enrolled, subjects must have clinically stable disease and treated with a prednisone dose of either 30 mg, 20 mg, or 10 mg (in accordance with their respective entry tier) for a minimum of 2 weeks before initiation of study drug and standardized taper. As such, the patient is not, by the physician's clinical assessment, showing signs of worsening disease (new symptoms or increasing severity of the symptoms that were observed at time of relapse) attributable to GCA. For example, a patient with relapse occurring at 30 mg prednisone may be increased to 40 mg/day for 2 weeks, 35 mg/day for 2 weeks and then 30 mg/day for two weeks. If deemed clinically stable on 30 mg/day prednisone after two weeks, the subject may enroll and begin study drug and standardized glucocorticoid taper. Additional examples: 1) if a relapse occurred at 15 mg/day, a patient may be increased to 20 mg for 2 weeks and if deemed clinically stable may undergo initiation of study drug after being on 20 mg for 2 weeks; 2) if a patient has previously been able to discontinue prednisone therapy and has a clinical relapse, prednisone can be re-initiated at 10 mg/day and if clinically stable at 2 weeks may proceed to enrollment. Once enrolled, subjects will begin study drug and reduce their prednisone dose on a standardized tapering schedule according to their respective entry dose (30 mg, 20 mg, 10 mg), as outlined in **Table 1**.

If a relapse occurs during the standardized taper (without evidence of severe ischemic event: defined as stroke, vision loss, critical limb ischemia) the patient will be removed from the standardized prednisone taper regimen but continue study drug for the remaining balance of the 52-week study period, provided no contraindication or criteria for study drug withdrawal is present at time of relapse. Once removed from the standardized prednisone taper, subsequent prednisone dose and management will be at the discretion of the treating provider. If a second relapse occurs, or if a relapse with the accompaniment of an aforementioned severe ischemic event is observed, then the study drug will be discontinued and prednisone and/or other alternative treatments will be provided as directed and at the discretion of the treating provider.

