5.5. Design Justification

This is a single-center, open-label study to evaluate the safety of baricitinib in GCA and to develop preliminary evidence of efficacy to support the potential conduct of a larger randomized trial.

The design of this study is similar in to other open-label phase II studies evaluating biologic medications in subjects with GCA [29, 38].

Glucocorticoids represent the only current standard of care treatment for patients with GCA. As such, prednisone will be continued during the initiation of the study drug. Subjects will enter the study at one of three doses of prednisone (30 mg, 20 mg, or 10 mg). Subjects should be on a stable prednisone dose for a minimum of 2 weeks (maximum 6 weeks) prior to initiation of study drug. Following study drug initiation prednisone tapering will occur in a standardized manner.

The 52-week study duration was chosen to assess for safety of medication use as well as to observe preliminary evidence of efficacy based on duration of glucocorticoid-free remission and relapse-free survival.

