5.6.4. Justification of Glucocorticoid Taper

Consensus guidelines recommend an increase in glucocorticoid treatment at the time of relapse to a previous higher dose, followed by repeat attempts at tapering once symptoms have improved/stabilized [40]. The protocol standardized tapering regimen is expedited compared to clinical practice in order to assess preliminary efficacy of the study drug.

Study subjects may enter the standardized taper at one of three levels; 30 mg, 20 mg or 10 mg. These strata were specifically designed to allow for appropriate increase of GC in response to the relapsing disease in a manner proportional to the dose of GC the subject was on at the time of relapse. It is common practice in treating relapses to increase GC to a prior dose in which the subject was asymptomatic. As such the three tier strata allows for clinicians to increase GC appropriately to achieve symptomatic control prior to a standardized taper instead of mandating

an increase to a required entry dose regardless of the GC dose at time of relapse. For example, it would be considered unnecessary, in the majority of circumstances, to increase a patient from 5 mg/day of prednisone to 30 mg/day for a moderate relapse of PMR symptoms, however an increase to 10 mg/day would be reasonable.

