11. STUDY ENDPOINTS

Primary endpoint:	
The primary endpoint is safety.
 
The measure by which this will be determined is the following:
 
 • Incidence of adverse events (AEs) and serious adverse events (SAEs) related to the study drug
Secondary endpoint	
The secondary endpoint preliminary efficacy of baricitinib (4mg, oral, daily) in patients with relapsing GCA.
 
The measures by which this will determined are the following:

	
 • Relapse-free survival at week 52 • Relapse-free survival at week 24 • Duration of glucocorticoid-free remission • Number of relapses per subject over time • Change from baseline erythrocyte sedimentation rate (ESR) to end of study • Change from baseline C-reactive protein to end of study • Glucocorticoid dose (mg) at week 52 compared to enrollment • Change in BVAS from baseline to end of study
--	---

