14. STATISTICAL ANALYSIS PLAN

The primary purpose of this pilot study is to evaluate the safety of baricitinib in subjects with GCA. No specific statistical hypothesis tests are planned. Safety data will be summarized for all treated subjects using appropriate tabulations, descriptive statistics, and graphical presentations. The incidence rate of each AE will be estimated and reported as number (n) and percentage (%).

Descriptive statistics will be provided for all secondary outcome measures. Differences between glucocorticoid dose (mg), C-reactive protein (mg/L), erythrocyte sedimentation rate (mm/hr) and BVAS score from baseline to end of study will be calculated and reported with means and standard deviations. The proportion of subjects in sustained remission will be reported with exact 95% confidence intervals. Kaplan-Meier methods will be used to evaluate relapse-free survival and the duration of glucocorticoid-free remission. Number of relapses per subject over time will be reported as relapses/year.

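### Do the pooled mean change in prednisone dose and the undated end of study for ESR, CRP and BVAS require a change to Section 14?

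*Combined protocol and SAP*

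**What the plan says.** Section 14 plans no hypothesis tests. It promises descriptive statistics for every secondary outcome. For prednisone dose, CRP, ESR and BVAS, the differences "from baseline to end of study will be calculated and reported with means and standard deviations". The same section plans Kaplan-Meier summaries of relapse-free survival and of the duration of glucocorticoid-free remission, and a proportion in sustained remission with an exact 95% interval.

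The dose endpoint has a date. Section 11 gives "Glucocorticoid dose (mg) at week 52 compared to enrollment" and Section 4 gives "Glucocorticoid dose (mg) at week 52 compared to baseline". The other three do not: Sections 1, 4 and 11 list, for example, "Change in BVAS from baseline to end of study", with parallel entries for ESR and CRP.

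On entry dose, Section 5.6.4 states: "Study subjects may enter the standardized taper at one of three levels; 30 mg, 20 mg or 10 mg". Table 1 takes these three levels to 0 mg at weeks 22, 19 and 15. Sections 9.6 and 9.11 and Table 2 schedule ESR, CRP and BVAS at both week 52 and week 64.

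**The concern.** A subject who is off prednisone at week 52 scores a change of exactly -30, -20 or -10 mg, according to entry level. The pooled mean therefore carries a component fixed at enrollment that has nothing to do with the drug. A reader could take a large mean reduction as a sign of efficacy when it partly reflects many subjects entering on 30 mg. The mean alone also does not show how many subjects came off prednisone.

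The visit matters because baricitinib stops at week 52. For a subject who completes treatment, the week-52 value is taken at the end of treatment and the week-64 value after 12 weeks without drug. In an open-label study, an unnamed visit leaves room to choose after the results are known. Section 14 also does not say which value an early stopper contributes. The trial is meant to support a decision about a larger randomized study, so a misleading summary would have some cost.

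**Working it through.** The plan gives no figure of its own for the dose change, so there is none to reproduce.

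**Prednisone dose**

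Inputs from the documents: 15 subjects (Section 5.2), entry doses of 30, 20 or 10 mg (Section 5.6.4), all tapers ending at 0 mg before week 52 (Table 1). Assumed, because the documents do not give them: the entry mix and the final doses of subjects not at 0 mg.

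The identity is: mean change = mean final dose - mean entry dose.

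Mean entry dose for three assumed mixes (numbers entering on 30/20/10 mg):
- 10/3/2: (300 + 60 + 20)/15 = 25.3 mg, SD 7.4 mg
- 5/5/5: (150 + 100 + 50)/15 = 20.0 mg, SD 8.5 mg
- 2/3/10: (60 + 60 + 100)/15 = 14.7 mg, SD 7.4 mg

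If ten subjects are at 0 mg and five on 10 mg, the mean final dose is 50/15 = 3.3 mg, whichever five they are.

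| Mix | All 15 at 0 mg | Ten at 0 mg, five on 10 mg |
|---|---|---|
| 10/3/2 | 0 - 25.3 = -25.3 mg | 3.3 - 25.3 = -22.0 mg |
| 5/5/5 | 0 - 20.0 = -20.0 mg | 3.3 - 20.0 = -16.7 mg |
| 2/3/10 | 0 - 14.7 = -14.7 mg | 3.3 - 14.7 = -11.3 mg |

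Within a column the final doses are identical, yet the means differ by up to 25.3 - 14.7 = 10.7 mg (from unrounded values). The order can reverse across columns: -22.0 mg with ten subjects off prednisone looks better than -14.7 mg with all fifteen off.

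Every such contrast is between two trials with different mixes. This trial has one arm and will have one observed mix. Within it, mean entry dose is a known constant, and the identity runs backwards: under the first mix, -22.0 + 25.3 = 3.3 mg recovers the mean final dose. The dose endpoint compares week 52 with enrollment, so describing it naturally involves both doses.

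**Which visit**

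Pointing to week 52:
- Section 14 puts dose under the same end-of-study phrase as the other three measures, and dose is fixed at week 52 in Sections 1, 4 and 11.
- Section 5.2 has relapsed subjects "continue study drug for the remaining balance of the 52-week study period".
- Section 5.5 says "The 52-week study duration was chosen to assess for safety of medication use" and goes on to give preliminary efficacy as the other reason.
- Section 5.1.2 describes the later phase as "A 12-week follow-up phase to ensure that all subjects are evaluated for safety at 12 weeks", so its stated purpose is safety.

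Pointing to week 64:
- Sections 5.2 and 9.12 count a subject as having completed only after the 12-week follow-up visit.

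Neutral:
- Section 9.12 also defines the end of the study as the last subject's last visit. That is a date for the whole trial and cannot serve as each subject's analysis visit.

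The balance favors week 52 without settling it. For subjects withdrawn early, Section 10.2 provides an early withdrawal visit and a 12-week follow-up, so late values are expected, but no section assigns one of them to the summary.

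**The case for a change.** The best case for a change is that it would be nearly free. Naming week 52, showing week 64 separately and adding rows by entry level would need no new visit. It would also remove a choice that could otherwise be made with the data in view. The other planned summaries do not quite replace a count of subjects at 0 mg: duration of glucocorticoid-free remission is a different quantity, and sustained remission is not among the definitions in Section 5.1.1.

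Much of this stands as description. The ambiguity is real for ESR, CRP and BVAS, the early-stopper rule is unwritten, and the pooled mean is easier to interpret with the entry counts beside it.

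It does not show that the plan as written yields a wrong or misleading result. Low cost is not by itself a reason to amend. The extra rows are a presentational preference with modest yield: with 15 subjects the cells by entry level are small, and 10 of 15 at 0 mg would carry an exact 95% interval of 38.4% to 88.2%. A 0-mg proportion among all treated subjects would also need its own rule for anyone without a week-52 dose, so it would bring back the early-stopper question.

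**Conclusion.** No change follows. The pooled mean change in dose is a correct, if not very informative, summary in a single-arm descriptive study. The 10.7 mg spread rests on assumed entry mixes and on final doses held equal across hypothetical trials. The entry mix cannot bias a comparison because there is no second arm and no planned test. Steroid-free status is largely covered by the Kaplan-Meier summary of glucocorticoid-free remission and the exact interval for sustained remission, with week-52 dose described against enrollment.

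The undated end of study for ESR, CRP and BVAS is an unwritten definition. It concerns a 12-week difference in assessment time for subjects who complete treatment. A sensible analyst would use week 52, in line with the dose endpoint, or report both visits, and would state how many subjects had a value and how early stoppers were handled. The documents give no basis for estimating how far the two visits would differ, so no numerical effect on those three outcomes is claimed. This conclusion assumes that the outcomes stay descriptive and secondary, as Section 14 says.

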15. PUBLICATION STRATEGY

This study will be registered with ClinicalTrials.gov prior to enrolling the first subject and the ClinicalTrials.gov Identifier (NCT#) will be included in manuscripts pertaining to this study. Results will be reported according to the requirements for applicable clinical trials.

Data generated from this study will be presented at national and international meetings pertaining to rheumatology (e.g. American College of Rheumatology and European League Against Rheumatism). Manuscript publication will target a high impact journal (Arthritis & Rheumatology).

